1.0 Background & Rationale

Chronic kidney disease (CKD) is a common chronic disease, affecting approximately 26 million American adults (1). CKD-mineral bone disorder (CKD-MBD) is a condition of disordered bone and mineral metabolism that contributes to morbidity and mortality in patients with CKD (2). CKD-MBD is characterized by the presence of all or some of the following features: laboratory abnormalities related to calcium and phosphorus homeostasis, bone disease, and vascular calcification. These abnormalities begin to appear early in the disease process (3), and virtually all patients with moderate to advanced CKD exhibit some or all features of the disorder. The clinical consequences of CKD-MBD are dire and include increased cardiovascular events, bone fragility fractures, and mortality (4-7). In fact, cardiovascular events are the leading cause of death in patients with CKD (8, 9). Thus, prevention and management of CKD-MBD is of critical importance to reduce morbidity and mortality in these patients. Calcium (Ca) and phosphorus (P) homeostasis are central to CKD-MBD development. ***However, lack of understanding on Ca and P metabolism in CKD-MBD progression precludes the development of effective therapies.***

Ca and P are intimately related in physiology and metabolism(10). They share common hormonal regulators that include parathyroid hormone (PTH), 1,25-dihydroxyvitamin D (1,25D), and fibroblast growth factor 23 (FGF23) that act on a common tissue axis of intestine, kidney, bone, and parathyroid glands. Treatments aimed at managing CKD-MBD affect the hormonal and tissue axes of both ions and have diverse effects on Ca and P serum levels. For example, calcitriol lowers serum P while increasing serum Ca (11, 12); whereas calcimimetics lower serum P while also lowering serum Ca (13). More importantly, serum or plasma

levels of Ca or P do not reflect whole-body status of either mineral (14, 15). This challenges both clinical research on Ca and P homeostasis, as well as clinical treatment decision-making. Thus, there is a **critical need** for knowledge of whole-body Ca and P physiology that can only be obtained from formal metabolic balance and kinetic studies of both ions simultaneously. However, such studies are largely absent in the scientific literature. Thus, **significant knowledge gaps** exist regarding whole-body Ca and P physiology that include how dietary Ca and P intakes, as well as kidney disease and its treatments, influence both Ca and P whole-body retention, intestinal absorption, and the transfer of Ca and P to and from the various body pools, such as intestine, bone, blood, and soft-tissue. Dietary P restriction is a commonly prescribed therapy for patients with CKD because it is presumed to reduce P retention and serum P, but this is based on little evidence (16). It is important to determine the effectiveness of dietary P restriction on its proposed benefits, because it is a difficult diet for patients to follow and may lead to consequences such as dietary protein or calcium deficiency, which can have negative consequences for bone health and mortality risk. The **goal** of this project is to generate preliminary data, including estimates of effect sizes and variances, on the effects of dietary P restriction therapy on Ca and P whole-body balance and full kinetics in patients with CKD. We will use this data in a future large research grant proposal that will include an adequately powered study to test the **hypothesis** that a high P diet, in the context of a typical low Ca diet, leads to P retention with negative Ca balance, and that dietary P restriction modestly reduces P retention but does not alleviate negative Ca balance. This will provide a foundation for further studies examining the effects of other factors on whole-body Ca and P physiology, including common pharmaceutical agents (e.g., various P binders, calcitriol, and calcimimetics), biological factors (e.g., age, race, and sex), CKD severity, and other nutritional interventions.

Additionally, preliminary and feasibility data will be collected on magnesium (Mg) absorption using stable oral and IV Mg isotopes (similar to the use of stable Ca isotopes). Dietary Mg and absorption is of interest in CKD patients as a potential inhibitor of calcification. Yet, to our knowledge, Mg absorption has not been studied in CKD patients (though stable Mg isotopes have been used for absorption studies in human subjects ranging from infants to postmenopausal women) (17-19).

2.0 Objectives

Aim 1. Determine intestinal Ca P, and Mg fractional absorption, effect sizes and variance estimates in patients with CKD on a low Ca diet with high P diet versus dietary P restriction. We will give CKD patients oral and IV Ca P and **and Mg** isotopes during a controlled-feeding, 48-hour inpatient study. In this study, we will use two dietary conditions and a randomized 2-period, cross-over design (low Ca/high P & low Ca/low P). Fractional Ca, P and Mg intestinal absorption will be determined by kinetic modeling of serum and urine oral and IV tracer data.

Aim 2. Determine Ca, P, and Mg balance and full kinetics, effect sizes and variance estimates in patients with CKD on a low Ca diet with high P diet versus dietary P restriction. A subset of subjects from Aim 1 will be studied as inpatients for an additional 12 days (5 as inpatient) after the 48-hour inpatient absorption testing protocol and in the same randomized 2-period cross-over design with the low Ca/high P & low Ca/low P diets. Total Ca, P, and Mg data will be determined from diet, urine, and fecal samples, and will be used to determine mineral balances. Further, we will use serum, fecal, and urine tracer data to determine full kinetic modeling including rates of transfer of the three ions between body pools, such as to and from bone.

3.0 Outcome Measures/Endpoints

3.1 Primary Outcome Measures

1. **Fractional Ca Absorption**, by kinetic modeling of Ca-44 isotopic data (by ICP-MS) over 48 hour between Days 8-10
2. **Fractional P Absorption**, by kinetic modeling of P-33 isotopic data (from scintillation counting) over 48 hour between Days 8-10
3. **Calcium Balance**, calculated from diet, urine, and fecal Ca assessed by ICP-OES, throughout Days 8-14

4. **Phosphorus Balance**, calculated from diet, urine, and fecal P assessed by ICP-OES, throughout Days 8-21(the last week is outpatient follow-up)
5. **Calcium Kinetics**, by full kinetic modeling of Ca-44 isotopic data (by ICP-MS), throughout Days 8-21(the last week is outpatient follow-up)
6. **Phosphorus Kinetics** by full kinetic modeling of P-33 isotopic data (by scintillation counting), throughout Days 8-21

3.2 Secondary Outcome Measures

1. **Fractional Mg Absorption**, by kinetic modeling of Mg isotopic data (by ICP-MS) over 48 hour between Day 8-10
2. **Magnesium Balance**, calculated from diet, urine, and fecal P assessed by ICP-OES, throughout Days 8-14
3. **Magnesium Kinetics** by full kinetic modeling of Mg isotopic data (by ICP-MS), throughout Days 8-21 (the last week is outpatient follow-up)
4. **Serum & Urine Ca** by standard clinical chemistry, all time points collected
5. **Serum & Urine P** by standard clinical chemistry, all time points collected
6. **Serum & Urine Mg** by standard clinical chemistry, all timepoints collected
7. **Serum Fibroblast Growth Factor 23, intact**, by ELISA kit, Day 1, all time points on Day 8-10, Day 15
8. **Serum Parathyroid Hormone, intact**, by ELISA kit, Day 1, all time points on Day 8-10, Day 15
9. **Serum 1,25-dihydroxyvitamin D**, by ELISA kit, Day 1, all time points on Day 8-10, Day 15

[figure not shown]
4.0 Eligibility Criteria

4.1 Inclusion Criteria

- Men or women, ages 30-75 years old, any race or ethnicity
- Moderate CKD, defined by KDIGO as eGFR category 3b (30-44 mL/min), with albuminuria categories A1-A3 (**Figure 1**)
- Female subjects must be postmenopausal (>12 months since last menstrual period), surgically sterile, or confirmed not pregnant by pregnancy test
- Must be on stable doses of medications (except those noted in exclusion criteria) for at least 4 weeks prior to the study
- Willing to discontinue nutritional supplements (e.g. vitamin D, calcium, multivitamin/minerals, or others) upon enrollment until completion of the study
- Adequate vitamin D status defined as serum 25D > 20 ng/mL

4.2 Exclusion Criteria

- Plans to initiate dialysis within 6 months
- Hypercalcemia defined as serum calcium >10.5 mg/dL within past 3 months
- Hyperkalemia defined as serum potassium >5.5 mg/dL within past 3 months
- Hyperphosphatemia defined as serum phosphate >5.5 mg/dL within past 3 months
- Intestinal disease that alters absorption or normal intestinal function including celiac disease, small bowel resection, or bariatric surgery
- Serious, *uncontrolled* underlying systemic disease including diabetes, lupus, hypertension (as deemed by the PI).
- Pregnant or breastfeeding
- Taking a phosphate binder medication, calcitriol, vitamin D analogs, calcimimetics, PTH analogues, and other medications that may alter Ca and P metabolism within past 30 days
- Vegan or vegetarian diet, lactose intolerance and/or milk allergy

Figure 1. Current CKD Nomenclature Used by KDIGO Guidelines

[figure not shown]
Green: low risk (if no other markers of kidney disease, no CKD); Yellow: moderately increased risk; Orange: high risk; Red, very high risk.

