6.0 Enrollment/Randomization

We aim to study N = 4 subjects, although seek approval enrolling up to 6 subjects due to the small sample size of 4 and the need for high adherence. Based on study diet and urine and fecal collection adherence of >90%, N = 2 patients that meet this level of adherence will be asked to continue with the full balance and kinetics protocol (Aim 2) on a first-enrolled basis. Thus 2 subjects will complete the absorption study (Aim 1), and 2 subjects will complete the full balance and kinetic studies (Aim 1 and Aim 2). It will be determined before a subject signs consent which consent they will sign (Consent A = Aim 1 or consent B= Aim 1 and Aim 2).

Recruitment will target moderate stage CKD patients aged 30-75 years old. Subjects will be recruited from patients seen in CKD clinics of the IU/Eskanazi Nephrology group who are partners of the co-investigators.

- Personnel from the IUSM Division of Nephrology will review medical charts from nephrology clinics for pre-screening to determine potential eligibility. An email will be sent to the doctors of the identified potential subjects to obtain their permission for enrollment and the potential subjects will be contacted by phone or visited by study staff during clinic.
- Information about the study may be discussed with interested potential subjects by research personnel by phone, email or in person as preferred by the subject/clinic.
- If interested, potential subjects will be either 1) scheduled for a screening visit at the Indiana Clinical Research Center, or 2) have screening information collected at the time of recruitment if subject is recruited in person at a CKD clinic by study staff.
- Prior to screening, subjects will be asked to provide written informed consent, and will be given the opportunity to have their questions about participation answered.
- Following the screening visit, all data will be evaluated by the study staff to determine eligibility of the subject. If eligible, participants will be enrolled in the study, and study visit dates will be scheduled.

Randomization Plan

At the beginning of the study, the study biostatistician will generate a randomization list for dietary intervention crossover order A or B by pairs. These orders will be A=LCa/HP to LCa/LP and B=LCa/LP to LCa/HP. Especially due to the small sample size, attention will be made to ensuring a balance of the two orders, which will be accomplished by randomizing both in pairs.

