7.0 Study Procedures

All study procedures will be conducted for the purpose of research.

Screening Visit

Following informed consent, a screening visit of approximately 60 minutes to assess eligibility will include a medical history, renal panel, and urine albumin/creatinine ratio (UACR). Recent lab values from the medical chart within ~3 months may be used if available. eGFR will be calculated from serum creatinine using the CKD-EPI equation (20). A urine pregnancy test of human gonadotropin will be performed for subjects of childbearing potential.

Pre-Study Washout Period and Run-In Period

Otherwise eligible subjects who take drugs that potentially alter calcium and phosphate balance or homeostasis including high dose cholecalciferol or ergocalciferol (1000 U/day or 50,000 U/wk, respectively), active vitamin D metabolites, calcimimetics, PTH analogues in the last 30 days, will undergo a 30-day pre-study washout from these drugs to be eligible for the study, with their physician approval.

All subjects will be given 600 IU/d of an oral vitamin D supplement (cholecalciferol) for 2-weeks prior to beginning the controlled feeding period and through completion of the study. This is to ensure vitamin D intake adequacy prior to the study, as was done for our previous balance study in CKD patients(14). 600 IU/d is the current recommended dietary allowance from the Institute of Medicine (18).

Dietary Interventions

The cross-over will consist of a randomly assigned order of two dietary conditions:

1) Low Ca (500 mg/d)/high P (1500 mg/d) diet (LCa/HP)

The LCa/HP diet is at levels within the range observed for a typical American diet poor in Ca and high in P (18-21)

2) Low Ca (500 mg/d)/low P (800 mg/d) diet (LCa/LP)

The LCa/LP diet represents coupling a typical poor Ca intake with the commonly prescribed dietary P restriction of 800 mg/d (22).

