For the full Ca, P, Mg balance and kinetics in Aim 2, a subset of N = 2 subjects will remain inpatient for an additional 5 days following the 48-hour absorption testing protocol described under Aim 1. During this time, all urine and fecal samples will be collected. Urine will be collected in time, 24-hour pools, as well as two 2-hour fasting urine collections taken on the morning of Day 15, aliquoted for fasting biochemistries, and then data combined with the appropriate 24-hour collection. Urine Ca, P, Mg and creatinine will be measured in each 24-hour collection or 2-hour fasting collection. Blood samples will be taken each morning, Day 10-15, to use for full Ca, P, and Mg kinetic modeling. Subjects will be discharged the morning of Day 15, after the 2-hour fasting urine and fasting blood collection; at this point they will discontinue study diet and PEG, but continue taking vitamin D at home for the remainder of Day 15 through Day 21. Fasting blood biochemistries will be measured in samples collected during a return outpatient visit on Day 21. In addition to isotope analysis, total serum Ca, P, Mg and creatinine will be measured by standard clinical chemistries. All fecal samples will be collected during the inpatient periods, then homogenized, ashed, and analyzed for Ca-44, P-33, Mg-25, Mg-26, total Ca, total P, total Mg, and PEG recovery.

Other Biochemistries

Additional biochemistries will be measured in serum and urine samples collected during these studies. These will include FGF23, PTH, 1,25D at the end of the study and creatinine clearances. The sequential and timed serum and urine samples will allow for dynamic assessment of these biochemical outcomes. Data on additional minerals Na, K, and Mg will be obtained from the ICP analysis of urine, diet, and feces, and may be used in secondary analyses. Additional analyses on leftover serum, urine, or feces may include other mineral metabolism biochemistries (e.g. 25-hydroxyvitamin D or bone turnover biomarkers), metabolites considered to be gut-derived uremic retention solutes (e.g. TMAO). The fecal microbiome may be analyzed in secondary analyses.

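### The hyperkalemia exclusion in Section 4.2 is printed with a potassium limit of 5.5 mg/dL (1.41 mmol/L), which read literally excludes every candidate

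*Combined protocol and SAP*

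**What the plan says.** Section 4.2 lists three consecutive exclusions based on serum chemistry, all with the same look-back period and all in mg/dL:

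- calcium: "Hypercalcemia defined as serum calcium >10.5 mg/dL within past 3 months"
- potassium: "Hyperkalemia defined as serum potassium >5.5 mg/dL within past 3 months"
- phosphate: "Hyperphosphatemia defined as serum phosphate >5.5 mg/dL within past 3 months"

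The potassium line is the only potassium limit in the documents. Potassium appears once more, in Section 7.0 under Other Biochemistries: "Data on additional minerals Na, K, and Mg will be obtained from the ICP analysis of urine, diet, and feces". That sentence concerns urine, diet and feces. It gives no serum value, limit or unit.

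The criteria are applied in Section 6.0. Nephrology personnel first pre-screen medical charts, and then: "Following the screening visit, all data will be evaluated by the study staff to determine eligibility of the subject".

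**The concern.** An exclusion limit for hyperkalemia should separate patients with raised potassium from the rest. The printed limit cannot do so, because it lies below any value that a living outpatient could plausibly have.

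Someone who follows the text enrols nobody. Someone who substitutes a sensible limit of their own enrols subjects who each formally meet a printed exclusion, and nothing on file says which limit was used. The population has eGFR 30-44 mL/min (Section 4.1) and the protocol chose to exclude for hyperkalemia, so the limit ought to be readable from the document. At stake is the correctness and traceability of one eligibility rule. The estimates that the pilot is meant to produce are not at stake.

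**Working it through.** No power, sample-size or alpha figure is involved, and the plan derives nothing from this limit. The check is a unit conversion.

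**Inputs**
- Printed potassium limit: 5.5 mg/dL (Section 4.2).
- Atomic mass of potassium: 39.098 g/mol (physical constant).
- Serum potassium values for comparison: assumptions, because the documents give no range. Three are used: a low value of 2.5 mmol/L, a usual range of 3.5 to 5.0 mmol/L, and a deliberately wide range of 2.5 to 6.0 mmol/L.

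**Step 1. Convert the printed limit.** mmol/L = (mg/dL × 10) / atomic mass.
5.5 × 10 / 39.098 = 55 / 39.098 = 1.41 mmol/L.

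**Step 2. Convert the assumed values to the printed unit.** mg/dL = mmol/L × 3.9098.

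| Assumed serum potassium | In mg/dL | Multiple of the printed 5.5 |
|---|---|---|
| 2.5 mmol/L | 9.8 | 1.8 |
| 3.5 mmol/L | 13.7 | 2.5 |
| 5.0 mmol/L | 19.5 | 3.6 |
| 6.0 mmol/L | 23.5 | 4.3 |

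Every value exceeds 5.5 mg/dL, including the lowest end of the widest range. The conclusion does not depend on which range is chosen: a candidate would need potassium of 1.41 mmol/L or less to escape the exclusion.

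**Step 3. Look for a correction elsewhere.** There is none. The one other mention of potassium (Section 7.0) carries no limit.

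**Step 4. Ask what the error is.** The phosphate line directly below has both the same number and the same unit, and the calcium line above has the same unit. A unit carried over from the neighbours would produce the printed line. So would a number and unit both carried over from the phosphate line. The text does not distinguish these explanations, so the intended limit cannot be recovered from it.

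**The case against.** The strongest reply is that this is a slip that nobody would act on. The criterion is headed as hyperkalemia, so its purpose is clear. Nephrology personnel pre-screen the charts, and the pilot plans 4 subjects with approval sought for up to 6. A literal reading that excludes everyone is one that no clinician would apply, and it rests on a physiological range that the documents do not state.

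Much of this stands. The practical effect is likely small, and the point should be weighted as a correction of wording, not as a flaw in the design. The reliance on an outside range is also real, but it matters little, since the margin is 1.8-fold even at a deliberately low value. What does not follow is that the line can stay. It is an operative criterion, complete and legible, with no sign of a redaction or a broken table, and the limit that staff would use in its place is written nowhere.

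A reader might go further and infer three things that the documents do not support.

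- *That recruitment, power or the diet contrast is compromised.* Nothing in the design or analysis uses the potassium limit, and no such effect can be shown.
- *That the intended limit is obvious, so that only the unit needs changing.* Step 4 of the working shows why the text cannot settle this.
- *That eligibility laboratory work is faulty more widely, because Section 4.1 requires* "Adequate vitamin D status defined as serum 25D > 20 ng/mL" *while the screening list in Section 7.0 names no 25D.* This does not amount to an error. Section 7.0 provides: "Recent lab values from the medical chart within ~3 months may be used if available". Section 10.0 budgets a 7 mL blood draw at screening. The Day 1 25D is listed as a baseline measure, and no section makes it the eligibility test. The visit-by-visit calendar is in Appendix B, which is not in the reviewed text, so a screening 25D cannot be called missing.

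**Conclusion.** The potassium limit in Section 4.2 is wrong as written. It equals 1.41 mmol/L, and read literally it excludes every candidate. The conversion is exact; the step to every candidate assumes only that serum potassium in eligible outpatients is above 1.41 mmol/L, which holds with wide room at the assumed low value of 2.5 mmol/L. Whether the number, the unit or both are at fault cannot be decided from the documents.

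The weight is low. It is an internal error in one eligibility threshold that staff would probably notice, with no consequence for power, sample size or the comparison of the two diets. The point does not extend to the calcium and phosphate limits, in which no error is shown, or to the 25D criterion.

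**What to change.** The sponsor should confirm the intended potassium limit and restate that single line of Section 4.2 in the unit that the clinical laboratory reports. Any screening log or eligibility checklist that repeats the printed limit should be brought into line. If subjects have already been screened, the limit that was actually applied should be recorded.

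The cost is one corrected line. No procedure, assay, sample size or analysis changes. This review does not propose a value for the limit.

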5.0 Study Design

The study design is a randomized 2-period cross-over study. **Figure 2** below describes the study timeline for participants enrolled in the study (a larger version is in attachments). All outpatient and inpatient visits will take place at the Indiana CTSI Clinical Research Center located in IU Health University Hospital in Indianapolis, IN.

For Aim 1, N = 4 subjects will be randomly assigned to controlled diets of either low Ca/high P (LCa/HP) or low Ca/low P (LCa/LP) for a 1-week, outpatient diet equilibration period, followed by a 48-hour inpatient Ca, P, and Mg absorption testing protocol. After a 1-3 week washout period, subjects only participating in Aim 1 (N = 2) will crossover to the other diet condition for another 1-week outpatient diet equilibration period, followed by another 48-hour inpatients Ca, P, and Mg absorption testing protocol.

For Aim 2, a subset of N = 2 subjects from Aim 1 will be studied as inpatients for an additional 5 days then a 7-day outpatient follow up for full Ca, P, and Mg balance and kinetic measures, after the 48-hour inpatient absorption testing protocol described under Aim 1. After a 1-3 week washout, they will crossover to the other diet condition for another 1-week outpatient diet equilibration period, followed by another 48-hour inpatient Ca, P, and Mg absorption testing protocol and additional 5 days inpatient and 7-day outpatient follow-up period for full balance and kinetics.

Figure 2. Study Timeline (larger version in Appendix)

